Endoscope Sterilization Procedures: The microendoscope is sterilized immediately after each procedure per standard endoscope accessory reprocessing guidelines. Any proflavine on the surface of the microendoscope is completely removed in the reprocessing procedure. This procedure has been approved by the FDA.

Patient Follow-Up for All Patients: All patients will recover from their procedures according to standard practice and be discharged home. To determine the safety of the HRME using topical proflavine, all pre, intra and immediate post-procedure adverse events will be recorded. Each patient will also receive a phone call from the research coordinator or co-investigator within 7 days from the study procedure to check for any post-procedure complications. In addition, prospective data will be collected on all patients at years 1,3,5 following index exam to determine whether they have progressed to a more advanced state of neoplasia.

Pathology Sample collection: Obtaining Tissue Samples from International Study Sites-Standard Operating Procedure

Biopsies from CICAMS and Jilin will be collected on H & E slides from clinical tissue blocks of all detected esophageal, high grade dysplasia and neoplasia.

The fixed biopsies will be oriented/embedded in paraffin and sectioned to facilitate comparison between histology and HRME images. Afterwards the serial sections will be routinely stained with hematoxylin and eosin for histopathologic examination.

The biopsies or resected specimens (from EMR) obtained from the examined areas will be routinely processed and interpreted by two expert GI pathologists ([name]) using standardized WHO classification criteria. Both pathologists will arrive at a consensus diagnosis which will be the official study read (gold standard).

The histopathologic diagnosis for each biopsy will be recorded on a standardized data collection form. The two central study pathologists will be reading ALL the specimens from China and the US and giving a consensus diagnosis. Image analysis will be performed comparing the actual histopathologic images to the "optical" images to develop image analysis algorithms and, potentially, image interpretations software. Rice University will be assisting in development of the image analysis algorithms for future software development.

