Diagnostic yield: This is defined as the proportion of all biopsies that are truly neoplastic over the total number of biopsies obtained in patients who receive biopsies. A generalized linear model for logistic regression with multiple correlated binary outcomes within each patient will be used for data analysis. In this model the binary outcome for each biopsy specimen is whether the specimen is neoplastic or non-neoplastic, and the explanatory variable is the arm (LCE+HRME vs. LCE alone) stratified by group (screening and surveillance). PROC GLIMMIX in SAS will be used because of the correlations among samples from the same patient. The model will allow for testing whether the proportion of samples classified as neoplasia differs between the 2 arms.

'Clinical efficiency': For patients that have benign disease confirmed by histology, the true proportion of patients potentially saved any biopsy using HRME (Lugol's + and HRME -) will be estimated by 95% confidence intervals (stratified by group). Proportions will be compared between groups by the chi-square test or Fisher's exact test. Procedure time in the HRME+LC arm will be compared to the LC arm by analysis of variance, stratified by group (screening and surveillance). An interaction term will also be included to determine to what extent the difference in procedure time between the 2 arms varies between the 2 risk groups.

Clinical impact: For this, the proportion of patients who had a change in the decision to perform endoscopic therapy or mucosal biopsies as a result of LCE+HRME or LCE alone, will be estimated by a 95% confidence interval. This proportion will be compared between LCE+HRME and LCE alone by the chi-square test or Fisher's exact test.

Progression rates: Five year follow-up of progression rates to more advanced pathology or esophageal cancer (EC) in the 2 arms will be conducted. Progression rates and their 95% confidence interval will be summarized and compared between LCE+HRME and LCE alone by the chi-square test or Fisher's exact test.

Safety/Adverse Events: Immediate and 48 hour adverse event (AE) rates will be compared between the LCE+HRME arm and LCE alone arm by the chi-square test or Fisher's exact test. The AE rates and their 95% confidence intervals will be summarized.

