Subjects will be consented on the day of their procedure. Subjects will be taken to a private area where the study information will be discussed. No additional sensitive information will be requested from the subjects beyond what is required to perform a standard surveillance endoscopy. Subjects will be given an ID number for all forms, images, and communications. All data will be coded. Source documents will be redacted of all PHI before being sent from outside sites for data monitoring/data entry in the database. All PHI collected on BCM subjects will be stored in locked cabinets or password-protected files/computers where only the PI and study coordinator can see the names. All case report forms will use the assigned subject ID. Since the subject participation is only for one visit, there will be limited opportunity for privacy interests to arise between study recruitment and end of the study. The only extra intrusion of privacy will be an additional phone call within 7 days of the procedure to ensure that the subject has not suffered any adverse events. During the follow-up, only the study coordinator and/or the PI will have contact with the subject. Information pertaining to the study will only be discussed with the subject and messages containing identifiers of the subject's participation will not be left on voice-mail messages.

For the post hoc image analysis project, the risk to the research subjects are minimal. Loss of privacy is an inherent risk, but to mitigate this, each subject will be assigned an unique, random ID and any identifying information will not be stored.

H2. Data and safety monitoring plan

Do the study activities impart greater than minimal risk to subjects?

Yes

NOTE: The answer to the questions in H2 requires the completion of the form: 'Section H – Data and Safety Monitoring Plan' as an attachment in Section S.

H3. Coordination of information among sites for multi-site research

Is the BCM Principal Investigator acting as the SPONSOR-INVESTIGATOR for this multi-site research?

Yes

Is BCM the COORDINATING CENTER for this multi-site research?

Yes

If the answer to EITHER of the questions above is "Yes", please complete the following questions:

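### The 48-hour adverse event rate does not match the way events are collected: the single call within 7 days has no earliest time, and events after 48 hours have no named comparison

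*Combined protocol and SAP*

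**What the plan says.** **Analysis.** Section G2 (Safety/Adverse Events) states: "Immediate and 48 hour adverse event (AE) rates will be compared between the LCE+HRME arm and LCE alone arm", by chi-square or Fisher's exact test. It adds: "The AE rates and their 95% confidence intervals will be summarized". It names no other safety window. Earlier in Section G2 the adverse event rate is listed among the secondary analyses, without a time limit.

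**Collection.** Section F2, under the heading "Patient Follow-Up for All Patients", states that "all pre, intra and immediate post-procedure adverse events will be recorded". For the time after discharge it provides a "phone call from the research coordinator or co-investigator within 7 days from the study procedure to check for any post-procedure complications". Section H1 (Loss of Privacy) describes the same contact as "an additional phone call within 7 days of the procedure to ensure that the subject has not suffered any adverse events", and notes: "Since the subject participation is only for one visit". The follow-up at years 1, 3 and 5 in Section F2 is there to detect progression of neoplasia.

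**The concern.** The analysis uses a fixed 48-hour window, while the only scheduled safety contact after discharge has a latest time but no earliest time. Two consequences follow.

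- A call at, say, 24 hours meets the protocol but tells the analyst nothing about hours 24 to 48. The plan does not say how such a patient enters the 48-hour rate.
- The call may find events that began between 48 hours and day 7. The protocol takes the trouble to look for them, yet the analysis plan names no rate or comparison that includes them.

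Section F2 gives the safety of HRME with topical proflavine as the reason for recording adverse events, and Section E1 classes the study as more than minimal risk with no prospect of direct benefit. A 48-hour rate that is too low, or late events left out of the comparison between arms, would weaken the safety statement the trial can make.

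**Working it through.** The documents state no expected adverse event rate, no power for safety and no distribution of call times, so there is no figure to reproduce. The check sets collection against analysis, taking hours from the procedure (an assumption; the plan does not define time zero).

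1. **Around the procedure.** Events are recorded (F2) and enter the immediate rate (G2). These match.
2. **Discharge to 48 hours.** Covered only by the call. If the call comes at 48 hours or later, the period is covered retrospectively. If it comes earlier, the period is covered only up to the call. The analysis (G2) treats 48 hours as a complete window.
3. **48 hours to the call, at most day 7.** Covered if the call is that late. G2 names no analysis for this period.
4. **Onset time.** To place an event reported on day 5 inside or outside 48 hours, its onset must be known. The text supplied does not mention recording it; the case report forms are not part of the text.

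**Illustration of how far timing matters.** Let t be the call time in days. The observed share of the 48-hour window is c(t) = min(t, 2)/2. The patterns of call timing below are assumptions, not figures from the documents.

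- Uniform over days 0 to 7: share called before 48 hours = 2/7 = 28.6%; mean coverage = (1 + 5)/7 = 85.7%.
- Uniform over days 1 to 7: share called early = 1/6 = 16.7%; mean coverage = (0.75 + 5)/6 = 95.8%.
- Uniform over days 1 to 3: share called early = 1/2 = 50%; mean coverage = (0.75 + 1)/2 = 87.5%.
- All at day 1: share called early = 100%; coverage = 1/2 = 50%.
- All at 48 hours or later: share called early = 0%; coverage = 100%.

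In these sums, 1 is the integral of t/2 from 0 to 2, 0.75 is the same integral from 1 to 2, and the last term is the number of days from day 2 to the end of the range, each with full coverage.

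Coverage translates directly into captured events only if events are spread evenly over the 48 hours. Events at or right after the procedure are recorded on site whenever the call is made, so if onset is concentrated there, the loss is smaller than these figures suggest. If a share f of events is captured in both arms, each rate and the difference between them is multiplied by f. The comparison is weakened, but it is not pushed towards either arm.

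**The case against.** The strongest reply is that the call goes to every patient in both arms, and that a call from 48 hours onward does cover the window. That stands. A reader might infer that nothing is collected for 48 hours, or that whatever the call finds goes unanalysed; neither is supported. Events reported in the call with onset by 48 hours can enter the 48-hour rate, and only later events lack a named comparison.

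A reader might also infer that patients called early are counted as event-free. No section says so; the plan is silent on their place in the denominator. Nor does anything show that call timing differs by arm. The same rule applies to both, and the documents give no ground for expecting bias between arms.

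Three further replies have some weight. Section H1 stresses that participants should tell study staff about side effects, so reporting need not end with the call; but unprompted reports do not replace a scheduled contact. The proflavine-specific reaction named in H1, anaphylaxis, is to be treated in the endoscopy room, so peri-procedural recording would capture it. The data and safety monitoring form mentioned in H2 is an attachment not supplied and may hold more detail, including onset times. Even so, F2, G2 and H1 would still need to agree.

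Finally, this is a secondary analysis, so the point is a modest one.

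**Conclusion.** The mismatch holds. As written, the protocol permits calls that leave the 48-hour window incomplete, so the 48-hour rate can be too low in both arms, and events with onset after 48 hours that the call finds have no named comparison. The direction is downward for the rates. The size cannot be given: it depends on when calls are made and when events start, and the documents state neither. Under the assumed timings above, coverage runs from 50% to 100%, which shows sensitivity to timing and is not an estimate of what will happen.

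The conclusion rests on the supplied text being the full account of safety contacts after discharge. The primary analyses of sensitivity, specificity and negative predictive value are not affected.

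**What to change.** Reconcile Sections F2, G2 and H1 as follows.

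- **Call window.** Word the single call so that it takes place at or after 48 hours and within 7 days. If that is not wanted, state that only patients contacted at or after 48 hours count as assessed at 48 hours. Apply that rule whether or not an event was reported, since keeping early-called patients only when they had an event would push the rate up. Give the number assessed in each arm.
- **Onset.** Record the date and time of onset of each event reported in the call, if the case report form does not already ask for it.
- **Analysis.** Keep the immediate and 48-hour rates, and add a by-arm comparison of all adverse events through the call (up to day 7), with 95% confidence intervals and the same tests. Tabulate call day by arm, because the length of observation varies with it.

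The cost is slightly less freedom in call timing and one more row in the adverse event table. No extra contact, visit or patient is needed. For patients already called before 48 hours, the assessed-at-48-hours rule can be applied where the time of the call was recorded.
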